
#### Stratification and Randomization

Those who complete the baseline assessment but are determined to be ineligible after baseline assessment will be given access to the online INSPIRE site as a courtesy. Those who meet all eligibility criteria will be randomized based on the stratification criteria described below. If any one of the following scores on baseline patient reported outcomes (PRO) is impaired, the participant will be randomized within 'Group 1,' if no scores are impaired the participant will be randomized within 'Group 0' for the primary and secondary endpoints: a) Cancer and Treatment Distress (CTXD score <0.9 vs.  $\geq 0.9$ ), b) cardiometabolic health care adherence (<80% vs.  $\geq 80\%$ ) and c) cancer health care adherence (<80% vs.  $\geq 80\%$ ). Note that each of these endpoints of the study has a measure cut-point for eligibility for Group 1 randomization required at baseline, and these are the threestratification parameters below. However, all eligible participants will be randomized

as they will all contribute data for secondary analyses. After minimum required baseline assessment is complete and eligibility confirmed, the Project Manager will fax the registration office with stratification data for randomization. Stratification factors are based on whether the participant exceeded or fell below the cut-offs for these endpoints, as determined by baseline screening values, prior to randomization. We will not stratify on age, sex, cGVHD treatment, or race/ethnicity because we believe these will be balanced adequately between study arms through random selection, and we will adjust, or stratify on these factors as needed in analyses. Participants in both groups will then be randomly assigned to either the "Control" or "Intervention" arms. The PIs and Biostatistician will review participation rates within each stratum annually and adjust the algorithm if needed. Once enrollment is complete, the sampling probability relevant to each participant will be stored in the database for use in analyses. Randomization assignment of the participant will be communicated to the participant through email. A diagram of study randomization is shown in Figure 2 and will occur as follows.

[figure not shown]
Group 1. Meets all eligibility and has one or more elevated distress or low cardiometabolic or cancer health care adherence and is randomized to one of the two groups, intervention or control.

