## Patient Reported Outcomes (PRO)

### Primary Outcomes

*Cancer and Treatment Distress (CTXD)*. The CTXD is a 22-item inventory of distress or worry related to stressful events for cancer survivors.[25] The measure was developed by the PI from structured interviews with HCT patients, nurses and physicians and has been tested with long-term survivors (N=1978). Testing supports its value as a predictor of health outcomes and it has been used in several RCTs.[6, 148-150] Internal reliability for HCT survivors is  $\alpha = .93$ . There are 6 reliable subscales: uncertainty, health burden, family strain, finances, medical demands, identity.[151]

*Health Care Adherence (HCA)*. The HCA is derived from the Cornell Service Index.[152] We have tested the format with several thousand HCT survivors.[153] Scores are transformed to proportion of HCA recommendations met. For a primary outcome, we use HCA items reflecting adherence to cardiometabolic surveillance (HCA-cardio; 5 items). Additional items measure adherence to subsequent malignancy surveillance (HCA-cancer; 7 items) and will be a secondary endpoint (see below). Items are adjusted for sex and age at which tests are recommended. An item is scored as 'adhered to' if the participant is under the age of recommended test onset. Cut point for determining adherence for each item is based on the frequency of testing recommended in guidelines (annual, every 3 or 5 years). Score is calculated as percentage of tests completed. Since adherence is important to reduce mortality risk, we set the cutoff for not meeting adherence criteria at <80%. In our previous 6-site INSPIRE study, we found 34% not adherent to HCA-cardio surveillance using the above criteria. Validity for HCA-cardio is supported by the following associations ( $p<.01$  for all):

HCA-cardio was higher in those with self-reported high blood pressure, diabetes, history of heart attack, and those told they had cardiomyopathy or atherosclerosis. Discriminant validity is supported by no significant association of HCA-cardio with report of a history of second cancers, osteoporosis, or thyroid problems. The 21 Barriers to HCA items were defined from qualitative patient reports of HCT survivors.[154] With 6 subscales, the overall and subscale reliabilities are all  $\alpha > 0.80$ . Mean score with cut point  $>0.45$  will be used as an Aim 2 predictor. with subscales: Cost, Avoidance, Time, Knowledge, Provider Access, .

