## Endpoints

The primary endpoints to be evaluated for the above hypotheses are CTXD (distress) and HCA-cardio. The primary and secondary endpoints for the study will be defined as binary outcomes. Participants will qualify for analysis of a particular endpoint if they meet eligibility at their baseline response for that endpoint (CTXD  $\geq 0.9$  or HCA-cardio  $<80\%$  [primary endpoints], or HCA-cancer  $<80\%$  [secondary endpoint], PHQ-8 score  $\geq 10$ ). Some participants will contribute to both primary endpoint analyses, and others to none or one. Similar conditional analyses will be carried out for the secondary endpoints. Stepped-care telehealth will be introduced based on PRO assessed at 6-weeks, then short term outcomes will be assessed after 3 months and delayed or sustained effects will be assessed at 1 year.

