### Power Calculations

As described in Table 3, we expect to enroll a total of 492 subjects in order to attain the 197 and 239 participants needed to meet eligibility criteria for Group 1 randomization and inclusion in the intervention vs. control arm analyses of the 2 primary outcomes: dichotomous CTXD and cardiac HCA outcomes, respectively (some will be eligible for more than one). Among these, we estimate that 71 and 86 per arm will be available for analyses after the 12-month evaluation, respectively. Assuming control arm rates of events similar to or higher than those observed in the preliminary data from the INSPIRE study, these numbers of participants will allow us to detect a minimum relative risk of success for the intervention arm vs. the control arm of 1.9 for the CTXD and for the HCA-cardio endpoints, with 80% power and two-sided  $\alpha=0.025$  for each comparison ( $\alpha=0.05/2 = 0.025$  to conserve overall  $\alpha=0.05$ ). For evaluation of the continuous versions of the outcomes, we will have at least 80% power to detect a minimum effect size of 0.52, and 0.47 for the CTXD and HCA-cardio outcomes, respectively ( $\alpha=0.025$  for each).

Table 3. Sample size calculations for Aim 1 primary outcomes, 80% power

### Analysis Plan for Hypothesis 1

The primary endpoints to be evaluated for hypothesis 1 are distress score (CTXD) and the proportion of HCA-cardio within the past 12 months as reported on the HCA and will be defined as binary outcomes.

Participants will meet the primary endpoint for lack of distress if they score <0.9 on the CTXD. They will

meet the HCA-cardio endpoint if their percent of recommended screenings obtained within the past 12 months is  $\geq 80\%$ . The number and pattern of missing variables will be summarized and assessed to understand potential biases. If attrition is greater than 10% before the 12-month follow-up, we plan to utilize multiple imputation of the primary outcome and to carry out sensitivity analyses of the impact of missing data on the comparisons between study arms.[173]

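### HCA-cardio is scored on guideline intervals in Section 8.2 but on the past 12 months in Section 12.7; if any cardio item has a 3- or 5-year interval, entry and success on this primary endpoint follow different rules

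*Combined protocol and SAP*

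**What the plan says.** Section 8.2 (Primary Outcomes, Health Care Adherence) makes HCA-cardio a five-item primary outcome, with seven further items forming HCA-cancer. Its item rule is: "Cut point for determining adherence for each item is based on the frequency of testing recommended in guidelines (annual, every 3 or 5 years". The score is a percentage, and below 80% is non-adherent. Younger participants get credit: "An item is scored as 'adhered to' if the participant is under the age of recommended test onset".

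Section 12.7 (Analysis Plan for Hypothesis 1) uses a different window. It names the endpoint as "the proportion of HCA-cardio within the past 12 months as reported on the HCA" and then sets the threshold: participants "meet the HCA-cardio endpoint if their percent of recommended screenings obtained within the past 12 months" is at least 80%.

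For baseline, Section 7.5 says "Stratification factors are based on whether the participant exceeded or fell below the cut-offs for these endpoints, as determined by baseline screening values", and Section 12.4 says "Participants will qualify for analysis of a particular endpoint if they meet eligibility at their baseline response for that endpoint". Both use the 80% cutoff and neither gives a look-back window.

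For HCA-cancer, Section 8.2 (Secondary Outcomes) adopts the HCA-cardio scoring, and Section 12.7 analyses it along the same lines as the primary endpoints.

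**The concern.** A test with a three- or five-year interval can be in date and still be more than 12 months old. Section 8.2 counts it as met; Section 12.7, as written, does not. The plan does not say that the five cardio items are all annual, that the 12-month window replaces the guideline interval at follow-up, or that the 12-month wording covers only tests falling due in that year.

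If any cardio item is multi-year, a survivor could enter the analysis under one rule and be judged under another, and two programmers could score the same survivor differently. This endpoint is one of two primaries, each tested at two-sided 0.025. Choosing between scorings after outcomes are seen would be hard to defend.

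**Working it through.** **The plan's own figures.** Table 3 carries 239 eligible participants to 239 × 0.72 = 172 completers, or 86 per arm. The detectable standardized effect is (z₀.₉₈₇₅ + z₀.₈₀) × √(2/86) = (2.241 + 0.842) × 0.1525 = 0.470, which matches the stated 0.47. These figures reproduce, but they do not show which scoring rule was meant.

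**Inputs.** Five cardio items and a success threshold of 80% (Sections 8.2 and 12.7). Since 3/5 = 60% and 4/5 = 80%, only four or five items met is a success.

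**Formulas.** At the 12-month assessment let a be the items met by a test in the past 12 months (under-age items counted as met), m the items met only by an in-date test older than that, and o the items not met, with a + m + o = 5.

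- Interval rule (Section 8.2): (a + m)/5
- 12-month rule, all five items in the denominator: a/5
- 12-month rule, only tests due that year in the denominator: a/(5 − m)

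| a, m, o | Interval rule | 12-month, all five | 12-month, due only |
|---|---|---|---|
| 4, 0, 1 | 4/5 = 80%, success | 4/5 = 80%, success | 4/5 = 80%, success |
| 3, 1, 1 | 4/5 = 80%, success | 3/5 = 60%, failure | 3/4 = 75%, failure |
| 4, 1, 0 | 5/5 = 100%, success | 4/5 = 80%, success | 4/4 = 100%, success |
| 3, 2, 0 | 5/5 = 100%, success | 3/5 = 60%, failure | 3/3 = 100%, success |

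**Direction.** The 12-month score never exceeds the interval score. On the first reading a/5 ≤ (a + m)/5. On the second, a/(5 − m) = 1 − o/(5 − m), which is at most 1 − o/5 = (a + m)/5 (for m = 5 it has no denominator). Successes under Section 12.7 are therefore equal or fewer.

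**Why the margin matters.** If baseline follows the interval rule, everyone analysed starts at 3/5 or lower. A survivor at 3/5 who gains one item lands on 4/5. A multi-year test that counted at baseline and was not repeated will be more than 12 months old a year later. If it is still in date, that survivor is the second row of the table.

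**If all five cardio items are annual.** Then m = 0, the rules coincide and the primary endpoint is untouched. Section 8.2 lists three- and five-year intervals, so the multi-year items would be among the seven HCA-cancer items. With seven items in the denominator, success needs six (5/7 = 71.4%; 6/7 = 85.7%). A survivor with a = 5, m = 1, o = 1 scores 6/7 = 85.7% under the interval rule, and 5/7 = 71.4% (failure) or 5/6 = 83.3% (success) under the two 12-month readings. This arises only if the 12-month window carries over to HCA-cancer, which Section 12.7 leaves open.

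**The case against.** The strongest reply is that the conflict is conditional. The interval list covers all HCA items, the three- and five-year tests may all be cancer tests, and nothing ties them to the cardio five. That stands, and it is why the point is worded conditionally.

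A second reply is that Section 12.7 is shorthand. Its first mention only names the endpoint and refers back to the HCA instrument, whose scoring is in Section 8.2. This is a fair reading of intent. But the 12-month wording recurs in the sentence that sets the success threshold, and a programmer following that sentence would not use guideline intervals.

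Three stronger readings are tempting and are not supported:

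- A reader might infer a second contradiction over under-age participants, since Section 12.7 speaks only of screenings obtained. Section 12.7 is silent on them, and silence does not override the explicit credit in Section 8.2. Section 8.2 itself calls the score a percentage of tests completed just after granting that credit.
- A reader might cite the prior-study result ("we found 34% not adherent to HCA-cardio surveillance using the above criteria") as proof that planning used the interval rule. Table 3 expects 239/492 = 48.6% eligible, whereas 34% of 492 is about 167. The documents do not explain the gap, and it cannot be attributed to either rule.
- A reader might infer lost power. The control rate is not given as a number: "Assuming control arm rates of events similar to or higher than those observed in the preliminary data from the INSPIRE study". With 86 per arm and relative risk 1.9, a control rate of 0.25 gives power 0.80 and 0.20 gives 0.64. Both rates are assumptions, and nothing shows that the relative risk would stay fixed when the scoring changes.

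**Conclusion.** The two sections state different look-back rules for a primary endpoint, and the plan does not reconcile them. This should be fixed before analysis. Whether it changes any HCA-cardio result depends on item intervals that the available text does not give. If all five items are annual, the effect on the primary endpoint is zero. If any is multi-year, a survivor at exactly 4/5 with one in-date test older than 12 months moves from success (80%) to failure (60% or 75%).

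The total effect cannot be determined: the intervals, the mix of 4/5 and 5/5 scores and the control rate are all missing. A reader might infer bias between arms, but both arms would be scored alike and none is shown. That Section 8.2 governs baseline is an inference, because Sections 7.5 and 12.4 give no window. Confidence is medium.

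**What to change.** Before outcome data are analysed:

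1. In Section 12.7, replace the 12-month window in both places with the Section 8.2 item rule: an item is met if done within its guideline interval, and under-age items count as adhered to. State that the rule applies identically at baseline and at 12 months.
2. State that HCA-cancer uses the same rule.
3. Add a table of the five cardio and seven cancer items with interval and age or sex onset. If all cardio items prove annual, one sentence closes the point for the primary endpoint.
4. Report 12-month scoring of the outcome as a sensitivity analysis in the same analysis set, stating whether tests not due that year stay in the denominator.

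Do not resolve the conflict by re-scoring baseline on a 12-month window. Baseline HCA-cardio helps to fix the Group 1 and Group 0 strata (Section 7.5), and only Group 1 intervention participants have the 6-week assessment and stepped-care calls (Sections 7.6 and 8.1). If any cardio item is multi-year, re-scoring could bring participants already randomized in Group 0 into the primary analysis without access to that component.

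The cost is wording, one table and a scoring-program check. No new data are needed if the HCA form records when each test was done, which is assumed because the form is not shown. The downside is that in-date tests done before randomization count as met, equally in both arms; the sensitivity analysis shows the result on recent testing alone.

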### Exclusion Criteria

- 4.2a** Development of invasive subsequent malignancy after HCT other than non-melanoma skin cancer, in the past two years.
- 4.2b** Medical or other issue prohibiting computer use, reading or ability to comply with all study procedures or unable to communicate via phone (e.g., significant vision, hearing or cognitive impairment, major illness, hospitalization).
- 4.2d** Residing in an institution or other living situation where health care decisions are not made by the participant (e.g., hospitalized, prisoners, living in a rehabilitation facility).
- 4.2e** Does not complete baseline PRO assessment items required to determine stratification or whether the survivor meets inclusion and exclusion criteria.
- 4.2f** Non-proficient in English (written and spoken).

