## Design

**Enrollment.** We expect to approach 1358 potentially eligible survivors who are between 2-5 years after HCT. Of these, 100 will be run-in approaches with a projected 20 enrolled and randomized, but not included in analyses. We project enrolling an additional N=492 eligible for a two-arm randomization to reach the sample sizes needed for each of the two primary endpoints. An additional projected 100 are expected to register and consent for the study, but either not complete baseline assessment required for randomization or to not be eligible for randomization after baseline assessment because of treatment in the past two years or other exclusion criteria. They will be given access to the INSPIRE site as a courtesy. We expect another group of 50 participants will consent but will not be eligible for randomization due to incomplete baseline assessment.

**Randomization.** Those with one or more targeted complications will be randomized to one of 2 arms (Group 1). Those without targeted complications will be separately randomized to one of 2 arms (Group 0). We expect approximately 305 will be eligible for Group 1 randomization and inclusion in one or more of the analyses of the 2 primary outcomes. To have sufficient power for each of the two primary endpoints, we will need to enroll 197 participants for the elevated distress outcome and 239 for the cardiometabolic non-adherence. Participants who do not qualify for analysis of either primary endpoint (Group 0) will be important for inclusion in secondary analyses and will also be randomized to intervention vs. control arms. Based on our experience in the previous internet grant, we project a loss of about 28% in the course of the study implementation from consent to 12-month assessment, 8% from mortality or severe medical problems. With 305 participants randomized to Group 1 for the primary analyses, this provides sufficient power for aims 1, 2, 3 and secondary analyses.

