For Hypothesis 1, the two primary endpoints, evaluated at the 12-month time point among the subjects identified at baseline as impaired for that particular endpoint criteria will each be compared between study arms as intent to treat analyses using standard logistic regression analyses, adjusted for cancer center and utilizing a two-sided  $\alpha=0.025$  level of significance to preserve type I error at 0.05 overall for the two primary endpoints. If other factors appear to be imbalanced between study arms, we will adjust analyses for those factors. Secondary analyses will evaluate depression alone, a PHQ-8 score  $\geq 10$  (essentially a subset of those with distress) and HCA-cancer in a similar manner as carried out for the primary endpoints. Continuous versions of the tests comprising the primary and secondary endpoints using linear regression models as well as adjusting or stratifying on engagement with the intervention (viewing at least 3 pages of the online program or completing telehealth calls) will also be carried out. Assumptions regarding normality of the outcomes will be assessed, although examination of outcomes in preliminary data suggests this is a reasonable assumption, with no significant skew in the distributions. If assumptions are not met, appropriate transformations will be implemented or alternative methods explored (e.g. non-parametric methods).

### Hypothesis 2

Characteristics of intervention arm participants at the 6-week interim assessment who require telehealth stepped care because they 1) do not meet criteria for adequate knowledge of subsequent malignancy and cardiometabolic risks, or 2) do not report improved distress, or 3) have not logged in to the online program will include those with higher depression or distress scores at baseline, more health care barriers at baseline, age 70+ years, male sex, people of color, lower income and education.

### Analysis Plan for Hypothesis 2

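### The primary test is valid but less efficient than it could be: it omits each endpoint's own baseline score and holds both endpoints at a fixed 0.025

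*Combined protocol and SAP*

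**What the plan says.** Under Analysis Plan for Hypothesis 1 (section 12.7), each primary endpoint is to be "compared between study arms as intent to treat analyses using standard logistic regression analyses, adjusted for cancer center", with a two-sided 0.025 "level of significance to preserve type I error at 0.05 overall for the two primary endpoints". No step-down rule is given. Centre is the only covariate named. The linear models for the continuous versions name no baseline covariate either.

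The baseline score of each endpoint is available before randomisation. Exclusion criterion 4.2e reads "Does not complete baseline PRO assessment items required to determine stratification or whether the survivor meets inclusion and exclusion criteria". Section 12.4 then uses that score to define the analysis sets: "Participants will qualify for analysis of a particular endpoint if they meet eligibility at their baseline response for that endpoint". The sets overlap: "Some participants will contribute to both primary endpoint analyses, and others to none or one".

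On missing data, section 12.2 says "we project a loss of about 28% in the course of the study implementation from consent to 12-month assessment", and section 12.7 says "If attrition is greater than 10% before the 12-month follow-up, we plan to utilize multiple imputation of the primary outcome". The variables of the imputation model are not listed.

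On further covariates, section 7.5 names age, sex, cGVHD treatment and race/ethnicity as factors that may be adjusted for where needed. Section 12.7 adds adjustment for any other factor that looks unbalanced. Neither section says what triggers the adjustment.

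**The concern.** Everyone in the CTXD analysis starts at 0.9 or above, and everyone in the HCA-cardio analysis starts below 80%. Within those sets, a participant just past the cut-off would be expected to reach the 12-month target more easily than one far from it. A model with arm and centre alone leaves that variation unexplained.

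The fixed 0.025 is a separate matter, because it concerns how alpha is used and involves no data. Once one endpoint is significant at 0.025, Holm allows the other to be tested at 0.05 with the same overall error. The fixed split gives that up.

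Hypothesis 1 names both reduced distress and better cardiometabolic adherence. What is at stake is power on each endpoint, and above all the chance of showing both, from the participants already planned.

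**Working it through.** **1. The plan's own figures.** Inputs from section 12.7 and Table 3: 71 and 86 completers per arm, two-sided 0.025, 80% power.
- The normal quantiles are 2.241 and 0.842, which sum to 3.083.
- Detectable standardised difference = 3.083 × √(2/n per arm). This gives 3.083 × √(2/71) = 0.52 and 3.083 × √(2/86) = 0.47, as stated.
- Completers: 197 − 8 − 9 − 38 = 142 and 239 − 10 − 11 − 46 = 172, as stated.
- The control rates behind the relative risk of 1.9 are not given in the readable text. Solving the two-proportion formula for 80% power gives about 28.0% (CTXD, 28% against 53%) and 24.9% (HCA-cardio, 25% against 47%). These rates are inferred.

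**2. Holm.** At noncentrality 3.083, power is 0.800 at 0.025 and Φ(3.083 − 1.960) = 0.869 at 0.05. With independent tests and the planned effect on both endpoints:
- One given endpoint: 0.800 + (0.869 − 0.800) × 0.800 = 0.855.
- Both: 0.869² − (0.869 − 0.800)² = 0.75, against 0.800² = 0.64 under the fixed split.
- At least one: 1 − 0.200² = 0.96 under either method.

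Simulation (4,000,000 draws) with test correlations 0, 0.2 and 0.4:
- Per endpoint: 85.6%, 85.2%, 84.8%.
- Both: 64.1% to 75.1%, 65.7% to 76.0%, 67.6% to 77.2%.
- At least one: 96.0%, 94.3%, 92.4%, unchanged by Holm.
- Other endpoint at half the planned effect: the stronger goes from 80% to 81-82%, the weaker from 24% to 32-33%.
- Other endpoint null: 80.0% to 80.2%.
- Family-wise error when both are null: 4.8-4.9% for both methods.

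The correlation range is an assumption. Section 12.2 expects "approximately 305 will be eligible for Group 1 randomization and inclusion in one or more of the analyses of the 2 primary outcomes". Reading 305 as the union of the two sets, 197 + 239 − 305 = 131 participants are in both. The test correlation is then 131/√(197 × 239) = 0.60 times the outcome correlation, so 0 to 0.4 covers outcome correlations up to 0.66.

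**3. Baseline score, binary test.** The correlation between baseline and 12 months in the full population is not in the documents, so a range is shown. Simulation: bivariate normal scores, baseline truncated to the worst 197/492 or 239/492, 12 centres as fixed effects, Wald test at 0.025. Completers: 10,000 runs. Multiple imputation (MI): 28% missing, 20 imputations, 3,000 runs, with the score in neither or in both of the imputation and analysis models. HCA-cardio has 5 items, so its baseline takes four values below 80%; here they are equally likely. Power (%) without and then with the score:

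| Correlation | CTXD completers | HCA-cardio completers | CTXD, MI, missing completely at random | HCA-cardio, MI |
|---|---|---|---|---|
| 0 | 78.1 to 78.2 | 79.0 to 78.7 | 75.9 to 75.7 | not run |
| 0.3 | 78.5 to 78.9 | 79.1 to 79.8 | 76.9 to 77.1 | 76.6 to 77.2 |
| 0.5 | 78.6 to 80.8 | 78.8 to 81.1 | 77.3 to 79.6 | 76.8 to 79.1 |
| 0.7 | 78.6 to 83.6 | 78.4 to 83.5 | 75.7 to 83.0 | 78.4 to 83.1 |
| 0.8 | 78.9 to 87.0 | 78.6 to 86.0 | 76.4 to 85.4 | 76.5 to 83.0 |

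If missingness rises with the baseline CTXD score, the gains at 0.7 and 0.8 are 79.3 to 83.1 and 79.1 to 86.3. Truncation weakens the correlation: full-population values of 0.3, 0.5, 0.7 and 0.8 become 0.17, 0.31, 0.48 and 0.60 within the CTXD set. If HCA-cardio scores cluster just below the cut-off (assumed 80/15/4/1% from 60% downward), its gain falls to about 1.5 points at 0.5 and 3 at 0.7.

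**4. Continuous versions.** The detectable effect shrinks by √(1 − r²), with r the within-set correlation. At r = 0.2, 0.4 and 0.6, 0.52 becomes 0.51, 0.48 and 0.42, and 0.47 becomes 0.46, 0.43 and 0.38.

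**The case against.** The plan is sound as it stands. A fixed 0.025 matches the alpha behind every stated power figure and gives simple simultaneous intervals. Holm does nothing for the chance of at least one success, and the documents do not say that both endpoints must succeed. All of this stands; it limits the value of Holm without giving a reason to prefer the fixed split.

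The covariate gain is uncertain, and this also stands. A reader might infer from the power figures that the correlation must be about 0.72 to 0.75, which would promise about 5 points. The documents do not support that. The inference needs control rates of 28% and 25% and an unchanged prevalence of impairment at 12 months. Section 12.7 allows control rates above those seen before, and at 40% the implied correlations are 0.50 (CTXD) and 0.34 (HCA-cardio). Section 8.2 reports 34% non-adherent on HCA-cardio, where Table 3 implies 239/492 = 49%. With 34%, the implied value is 0.84 at a 25% control rate and 0.59 at 40%. A check that runs from about 0.34 to 0.84 settles nothing.

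A prognostic covariate also changes the conditional odds ratio, while power is stated as a relative risk. That is correct, so the effect measure must be named. The other two baseline cut-offs, which section 7.5 calls stratification parameters, still vary within each set. Whether to add them was not examined here.

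The clause on unbalanced factors does not cover the point, since a balanced but prognostic score would never enter through it.

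**Conclusion.** The point holds as an efficiency improvement to a valid test.

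The Holm gain does not depend on the missing correlation and cannot be negative. At the planned effect on both endpoints it is 5 to 6 points per endpoint and about 10 to 11 points for both. It falls to about 0.2 points if the other endpoint has no effect. It rests on the stated 80% power and on test correlations of 0 to 0.4; error control holds under any dependence.

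The baseline-score gain is about 0 to 1 point at a full-population correlation of 0.3 or below, about 2 at 0.5, about 5 at 0.7 and 7 to 9 at 0.8. It may be less for HCA-cardio if its few levels cluster near the cut-off. The documents do not show which value applies.

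A reader might infer that the present plan inflates type I error. It does not: 0.025 + 0.025 = 0.05, and no inflation from the imbalance clauses is shown. A reader might also infer that the adjustment factors are nowhere listed, but section 7.5 does list four. What is missing is a rule for when they enter, and the further factors in section 12.7 are open-ended. That part concerns pre-specification only.

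**What to change.** Amend section 12.7 before any comparison of outcomes by arm:

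1. Pre-specify arm, centre and the baseline score of the endpoint analysed in both the logistic and the linear models. List the same variables in the imputation model, since the projected 28% loss exceeds the 10% trigger.
2. Name the effect measure to be reported, for example a standardised (marginal) relative risk from the logistic model, so that the result matches the scale of the power statement.
3. Replace the fixed 0.025 with Holm: test the smaller p-value at 0.025 and, if it is significant, the other at 0.05.
4. Keep this covariate list as primary. Move adjustment prompted by imbalance (sections 7.5 and 12.7) to a sensitivity analysis.

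The cost is SAP wording; no new data are needed. Simultaneous confidence intervals become less simple under Holm. Wald tests with 12 centre terms are slightly liberal among completers, and the score hardly alters this: simulated size is 2.6-3.2% with it and 2.6-3.0% without, against a nominal 2.5%. Under multiple imputation size is 2.1-2.9% either way.
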